# 10.5.3. Subgroup Analyses

PFS will be reported for each level of stratification factor and baseline covariate to check the homogeneity of treatment effect across levels of factors as defined in the statistical analysis plan. Median values for each level of factor will be computed using Kaplan-Meier estimates. Cox

proportional hazards model will be used to calculate hazard ratios and CIs. Forest plots will be generated to display hazard ratio treatment differences across subgroups which will be defined in the SAP.

#### 10.5.4. Safety Analyses

Safety analyses (adverse events and laboratory analyses) will be performed using the safety population. Adverse events will be coded using the latest MedDRA dictionary. Severity of adverse events will be graded according to the NCI CTCAE version 4.03.

Treatment-emergent adverse events (TEAEs) are defined as any event that occurred after the first dose of study drug and was not present prior to study drug administration or worsened in severity after study drug administration. TEAEs will be collected through the end of treatment visit. Frequency and percent summaries will be presented for treatment-emergent adverse events (TEAE) defined as adverse events that occur or worsen in severity following the first dose of seribantumab, or fulvestrant. Additional tabulations include serious adverse events (SAE), TEAE-related to seribantumab, fulvestrant and TEAE grade  $\geq 3$ , and discontinuation due to TEAE. Adverse events will be summarized by System Organ Class and preferred term. All adverse event data will be listed by patient.

Maximum and minimum decrease in continuous laboratory data will be reported. Bar graphs depicting treatment arms will be reported. Frequency and percent of abnormal laboratory values (L/ULN, 2\*L/ULN) will be assessed. Shift to most severe toxicity grade will be summarized.

Vital signs, ECG, and ECHO/MUGA will be tabulated for the change from baseline by time point. Additional analyses may be performed as described in detail within the SAP.

# 10.5.5. Biomarker Analyses

Biomarker data will be explored from collected tissue, as well as serum and whole blood samples, to assess potential associations with tumor response. These samples will be used to assess additional clinically relevant biomarkers. PFS, ORR, and TTP may be considered for exploratory biomarker analysis. Kaplan Meier methods for displaying graphs and Cox proportional models will be used when estimating hazard ratios with 95% confidence intervals. Biomarker analyses will be further detailed in the SAP.

### 10.5.6. Pharmacokinetic Analyses

Serum concentrations will be used to determine PK parameters for seribantumab and fulvestrant as appropriate using population pharmacokinetic analysis. The resulting PK parameters will be associated with efficacy and safety endpoints as appropriate. Details will be provided in a separate population PK analysis plan.

# 10.6. Data Monitoring Committee

An independent Data Monitoring Committee (DMC) will be established to regularly monitor emerging safety data and evaluate for trial efficacy as outlined in the DMC charter. The DMC will consist of oncology and statistical experts, independent of the Sponsor. The DMC will be unblinded to randomization information. The charter of the DMC and the statistical analysis plan will be documented separately.

#### 11. Study Administration

## 11.1. Pre-Study Documentation

Prior to initiating the trial, the investigator will provide the Sponsor or designee with the following documents:

- A signed FDA Form 1572 (or equivalent information for ex-US sites that do not permit completion of the U.S. FDA 1572 form).
- A current (i.e. updated no more than 24 months prior) curriculum vitae for the Principal Investigator and each sub-investigator listed on the FDA Form 1572 or equivalent, that is signed and dated.
- A copy of the current medical license for the investigator and each sub-investigator.
- A letter from the IRB/EC stipulating approval of the protocol, the informed consent document, and any other material provided to potential trial participants with information about the trial (e.g. advertisements)
- The current IRB/EC membership list for the reviewing IRB/EC, or the multiple project assurance number from the U.S. Federal Wide Assurance program where applicable
- A signed Investigator Protocol Agreement
- A completed financial disclosure form for the investigator and all sub-investigators
- A current laboratory certification for the local reference laboratory and curriculum vitae of the laboratory director
- A list of current laboratory normal values for the reference laboratory

#### 11.2. Source Documents

The investigator will maintain records separate from the case report forms in the form of clinic charts, medical records, original laboratory, radiology and pathology reports, pharmacy records, etc. The investigator will document in the clinic chart or medical record the date on which the patient signed informed consent prior to the patient's participation in the trial. Source documents must completely reflect the nature and extent of the patient's medical care, and must be available for source document verification against entries in the case report forms when the Sponsor's monitor visits the investigational site. Source documents regarding procedures such as scans and laboratory evaluations performed as part of the standard of care prior to enrollment in the study can be used to fulfill certain screening and baseline assessments. All information obtained from source documents will be kept in strict confidentiality. Source data sent to the Sponsor or the Sponsor's representative as supporting documentation for serious adverse events will be deidentified to preserve confidentiality.

#### 11.3. Trial Ethics

The study will be performed according to the principles of the Declaration of Helsinki, the International Conference on Harmonization Guidance on Good Clinical Practice and the requirements of the US FDA and/or local regulatory authorities regarding the conduct of human clinical trials.

#### 11.4. Patient Informed Consent

No study related procedures will be performed until a patient or a patient's legal representative has given written informed consent. The Sponsor will provide to the investigator a sample

informed consent document that includes all the requirements for informed consent according the ICH GCP, U.S. FDA guidelines (21 CFR 50) and/or local regulatory guidelines. However, it is up to the investigator to provide a final informed consent that may include additional elements required by the investigator's institution. Changes to the Sponsor's sample informed consent should receive approval from the Sponsor or the Sponsor's representative prior to use in the study. The informed consent document must clearly describe the potential risks and benefits of the trial, and each prospective participant must be given adequate time to discuss the trial with the investigator or site staff and to decide whether or not to participate. Each patient who agrees to participate in the trial and who signs the informed consent form will be given a copy of the signed, dated and witnessed document. The provision of informed consent must be documented in the medical record.

## 11.5. Investigational Review Board Approval

The trial will not be initiated until there is approval of the protocol, informed consent document and any other material used to inform the patient about the nature of the trial by the local IRB or EC. The IRB or EC should be duly constituted according to local regulatory requirements. Approval must be in the form of a letter signed by the Chairperson of the IRB/EC or the Chairperson's designee, must be on IRB/EC stationary and must include the protocol by name and/or by designated number. If an investigator is a member of the IRB/EC, the approval letter must stipulate that the Investigator did not participate in the final vote, although the investigator may participate in the discussion of the trial. The investigator will also inform the IRB/EC of any SAE that the Sponsor reports to regulatory authorities, will report on the progress of the trial at least yearly (or more frequently if required by local regulation or guidance) and will provide to the IRB/EC a final summary of the results of the trial at the conclusion of the trial.

#### 11.6. Monitoring

Overall study monitoring will be conducted through a combination of on-site visit and centralized monitoring. A risk-based, data-driven monitoring approach will be used to verify data for this trial which will also include a centralized review of data for quality, trends, consistency and general safety review. A clinical monitor will make regularly scheduled trips to the investigational site to review the progress of the trial, study data and site processes. At each visit, the monitor will review various aspects of the trial including, but not limited to: screening and enrollment logs; compliance with the protocol and study manual and with the principles of Good Clinical Practice; completion of case report forms; source data verification; study drug accountability and storage; facilities and staff.

The actual frequency of monitoring trips will depend on the enrollment rate and performance at each site. The investigator will allow Merrimack Pharmaceuticals, and/or its representatives or designees, access to all pertinent medical records, as required by federal regulations, in order to allow for the verification of data gathered in the CRFs and for the review of the data collection process.

During scheduled monitoring visits, the investigator and the investigational site staff must be available to meet with the study monitor in order to discuss the progress of the trial, make necessary corrections to case report form entries, respond to data clarification requests and respond to any other trial-related inquiries of the monitor. In addition to on-site monitoring visits, the Sponsor and/or representatives will also be routinely reviewing data. Any queries identified

through this review will be managed within the systems established for query resolution and tracking. Inquiries related to study conduct which require further information or action will be discussed within the study team for appropriate and documented escalation plans. It is expected that response to data clarification requests and other trial-related inquiries will occur throughout the course of the study through regular communication with the site monitor, the Sponsor or representatives, and review/entry of data into the electronic study database.

At any time during the course of the study, representatives of the FDA and/or local regulatory agencies may review the conduct or results of the study at the investigational site. The investigator must promptly inform Merrimack Pharmaceuticals of any audit requests by health authorities, and will provide Merrimack Pharmaceuticals with the results of any such audits and with copies of any regulatory documents related to such audits.

In accordance with HIPAA and associated privacy regulations, a patient's authorization to use personal identifiable health information may be required from each patient before commencement of research activities. This authorization document must clearly specify what parties will have access to a patient's personal health information, for what purpose and for what duration.

# 11.7. Confidentiality

It is the responsibility of the investigator to ensure that the confidentiality of all patients participating in the trial and all of their medical information is maintained. Case report forms and other documents submitted to the Sponsor must never contain the name of a trial patient. All patients in the trial will be identified by a unique identifier which will be used on all CRF's and any other material submitted to the Sponsor. All case report forms and any identifying information must be kept in a secure location with access limited to the study staff directly participating in the trial.

## 11.7.1. Confidentiality of Biomarker Samples

Blood and tissue samples collected as part of the biomarker analysis will be identified only by a number assigned to the patient at the study site; this number will be used in lieu of the patient's name in order to protect the patient's identity. The samples will be stored at a facility designated by the Sponsor. Other than the patient's unique identifying number, no additional patient information will be stored with these samples. Samples will be kept until they are used completely for the specified biomarker analyses, or, in the event there is remaining tissue or blood sample available, such specimens may be stored indefinitely. At the time of informed consent, patients will be able to refuse indefinite storage of these remaining samples. If indefinite storage is refused, any remaining samples will be destroyed following the completion of the study. Similarly, patients may withdraw approval at any time by submitting a written request to the study site investigator. Upon receipt of this withdraw of consent, no further analyses will be completed and the patient's remaining samples will be destroyed; however, data already collected will not be removed from the study dataset.

Any samples that a patient consents to be stored indefinitely may be used by the Sponsor for future oncological translational work, as directed by the findings of the exploratory biomarker evaluation and the results of the initial tissue biomarker evaluation. The results from these exploratory analyses may not necessarily be shared with the investigators or the participating subjects.

#### 11.8. Protocol Amendments

The protocol will only be amended with the consent of the Sponsor and the IRB/EC. Changes to the protocol must be in the form of a written amendment; changes other than those of a simple administrative nature (e.g., a new telephone number for a medical monitor) must be submitted by the investigator to the local IRB/EC and such amendments will only be implemented after approval of the requisite IRB/EC. All amendments will also be submitted to the FDA and/or local regulatory authorities by the Sponsor.

Protocol changes to eliminate an immediate hazard to a trial patient may be implemented by the investigator immediately. The investigator must then immediately inform their IRB/EC and the Sponsor will immediately notify applicable regulatory authorities.

### 11.9. Records Retention

The investigator will retain the records of the clinical trial (including, but not necessarily limited to, CRFs, source documents, informed consent forms, drug accountability records, IRB/EC correspondence, Sponsor correspondence, etc.) for 2 years following the date that the last marketing application for the study drug is approved (or per local regulatory requirements), or if no marketing application is filed, or if such an application is not approved, for 2 years after the formal discontinuation of clinical development of the study drug. The Sponsor or designee will notify investigators when retention of study records is no longer required. Study records must be stored in a safe and secure location permitting timely retrieval, if necessary.

Study records must be retained as per the GCP guidelines and local regulatory requirements, including, but not limited to, case report forms, signed informed consents, correspondence with the IRB/EC, study drug dispensing and inventory records, source documents (clinic charts, medical records, laboratory results, radiographic reports) and screening/enrollment logs.

Should the investigator relocate or retire the responsibility for maintaining the study records may be transferred to another investigator. The Sponsor must be notified of the identity of the individual assuming responsibility for maintaining the study records and the location of their storage. If no other individual at the site is willing to assume this responsibility, the Sponsor will assume responsibility for maintaining the study records.

# 11.10. Study Termination

The Sponsor reserves the right to terminate the study at any site and at any time. Reasons for study termination may include, but are not limited to, the following

- Investigator non-compliance with the protocol, GCP or regulatory requirements
- Insufficient enrollment
- Safety concerns
- Drug supply or manufacturing issues
- The Sponsor's decision to modify or discontinue the development of seribantumab
- A request to discontinue the study by the FDA and/or local regulatory authorities

The Sponsor will promptly inform all investigators and the FDA and/or local regulatory authorities if the study is suspended or terminated for any reason. The investigator will promptly notify the IRB/EC if the study is suspended or terminated.

# **ABBREVIATIONS**

AE	Adverse event
AUC	Area under the curve
BSA	Body Surface Area
CBR	Clinical benefit rate
CI	Confidence Interval
Cmax	Maximum serum concentration
CR	Complete Response
CRF	Case report form
CSR	Clinical study report
CT	Computed tomography
CTCAE	Common terminology criteria for adverse events
DMC	Data Monitoring Committee
DOR	Duration of Response
DSMB	Data Safety Monitoring Board
ECG	Electrocardiogram
ECHO	Echocardiogram
eCRF	Electronic case report forms
EDC	Electronic data capture
FDA	Food and Drug Administration
HRG	Heregulin
ICH	International conference on harmonization
ITT	Intent-to-Treat
IWRS	Interactive web response system
LVEF	Left ventricular ejection fraction
MedDRA	Medical Dictionary for Regulatory Activities
Mth	Month
MUGA	Multiple gated accession scan
NCI	National Cancer Institute
NE	Not Evaluable
ORR	Objective response rate
OS	Overall Survival
PD	Progressive disease
PFS	Progression free survival
РК	Pharmacokinetic
PR	Partial response
РТ	Preferred term
QTcF	Fridericia's QT correction
RECIST	Response Evaluation Criteria In Solid Tumors
SAE	Serious adverse event

Version Date: 29Jan2016

SAP	Statistical Analysis Plan
SD	Stable Disease
SOC	System Organ Class
SRB	Safety Review Board
Tmax	Time to maximum serum concentration
t 1/2	Terminal elimination half-life
TFL	Tables, Figures, Listings
TTF	Time to treatment failure
ULN	Upper limit of normal
Vdss	Volume of distribution at steady state
Wk	Week

## **1. INTRODUCTION**

This is the Statistical Analysis Plan (SAP) for protocol seribantumab-02-03-10.

## 1.1 Protocol Changes and Clarifications

No previous signed off SAP versions have been written as of the current sign-off. The following are clarifications for protocol analysis.

## 1.2 Study Design

This study is a double-blind, placebo-controlled, phase 3 trial of exemestane or fulvestrant with or without seribantumab in postmenopausal patients with hormone receptor-positive, heregulin positive (HRG+), HER2 negative metastatic breast cancer whose disease progressed after prior systemic therapy.

## 1.3 Study Objectives

The primary objective of this study is to determine whether the combination of seribantumab plus exemestane or seribantumab plus fulvestrant is more effective than placebo + exemestane or placebo + fulvestrant based on investigator assessed Progression Free Survival (PFS) in HRG positive patients (defined as HRG ISH score of  $\geq 1+$ ).

The secondary objectives of this study are as follows:

- To determine whether the combination of seribantumab plus exemestane or seribantumab plus fulvestrant is more effective than placebo + exemestane or placebo + fulvestrant in HRG positive patients for the following clinical outcome parameters:
  - Time to Progression (TTP)
  - Objective Response Rate (ORR) based on RECISTv1.1
  - Overall Survival (OS)
- To compare the time from randomization to subsequent chemotherapy between the seribantumab containing arms and the comparator arms of the study To describe the safety profile of seribantumab in combination with exemestane or fulvestrant
- To describe the safety profile of seribantumab in combination with exemestane or fulvestrant
- To assess health-related quality of life (HRQOL) using EuroQol 5-Dimension (EQ-5D-5L), Functional Assessment of Cancer Therapy Breast (FACT-B) and Brief Pain Index (BPI) questionnaires
- To characterize the pharmacokinetic (PK) profile of seribantumab when given in combination with exemestane or fulvestrant and of exemestane or fulvestrant when given in combination with seribantumab
- To assess the effect of seribantumab on ECG parameters

The exploratory objectives of this study are as follows:

- To assess the correlation for HRG expression between fresh tissue biopsies and archival samples where available
- To estimate resources required for hospitalization

## 2. Analysis Sets

## 2.1 Intent-to-Treat (ITT)

The ITT population will include all patients who are randomized, with study drug assignment via an Interactive Web Response System (IWRS), irrespective of whether patients receive the intended study drug or a different drug than

allocated through randomization. ITT patients with central lab HRG positive (1+, 2+, 3+, 4+) results will be considered the primary efficacy population. Patients with missing or indeterminate HRG or HRG negative will not be part of the ITT primary efficacy population.

## 2.2 Safety Population (SAF)

This will include all patients in the study receiving at least 1 dose of study drug. These patients will be defined as the safety population.

## 2.3 Pharmacokinetic (PK)

This population includes all SAF patients with at least 1 on-treatment PK assessment.

## **3. ENDPOINTS**

## 3.1 Progression-Free Survival – Investigator Assessed

Investigator Assessed (IA) tumors assessments are those determined by the investigator. PFS is defined as the number of months from the date of randomization to the date of death or documented (objective) disease progression via RECISTv1.1, whichever occurs earliest. Length of PFS will be calculated in days and reported in months.

[Progression/Death/Censor Date - Randomization Date + 1] / 30.4375.

The tumor assessment (i.e., scan dates) will be used for progression/censor date not the date corresponding to the determination of overall response. When multiple dates occur for assessing target, non-target, and new lesions the following rule will be applied:

- If documented disease progressions, the *first* available date will define the tumor assessment date
- If censored, the *last* available date will define the tumor assessment date.

Per protocol tumor assessments are scheduled to be performed every 8 weeks ( $\pm$  7 days) from day of first dose until investigator-assessed progression, in addition to a 30-day follow-up.

**Censorship**: In general, patients are censored at the date of the last tumor assessment that verified lack of disease progression if they are last known to be alive, on-treatment or within 30 days following treatment discontinuation, and progression-free. Censoring is explicitly described below and in table 1. Patients that do not experience progression or death by the time of analysis (data cut-off) will be censored at the date of last tumor assessment defined by any overall response other than "not evaluable".

- Patients with an inadequate/incomplete baseline tumor assessment will be censored at the date of randomization
- Patients with no tumor assessment after dosing will be censored at the date of randomization unless death occurred prior to the first planned assessment (in which case the death is an event)
- Patients with at least one on-study disease assessment who discontinue treatment without documented disease progression or death are censored at the date of the last tumor assessment

There are two exceptions.

- $\circ$  Documented progression or death  $\leq$  30 days after treatment discontinuation then progression or death is an event
- A new anti-cancer treatment is started prior to documented progression and ≤ 30 days after treatment discontinuation, then censorship is at the date of the last tumor assessment that verified lack of disease progression prior to the new treatment
- Patients with documentation of progression or death after an unacceptably long interval (i.e., 2 or more consecutively missed or indeterminate/not evaluable assessments) since the last tumor assessment will be censored at the date of last tumor assessment documenting no progression

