on the date of randomization. Patients starting a new anti-cancer treatment prior to documented PD will be censored at the date of the last observed tumor assessment prior to start of the new treatment. Patients with documented PD or death after an unacceptable long interval (i.e., 2 or more missed or indeterminate scheduled assessments) will be censored at the time of the last observed tumor assessment date. PFS will be calculated as the date of the event/censor minus date of randomization plus one.

The primary analysis will be performed using a stratified log-rank test comparing the PFS difference between two treatment arms. The final PFS analysis will preserve the 1-sided alpha at 0.10. Stratification factors will include bone-only disease (yes, no) and geographic status (US, and non-US). Kaplan-Meier estimates will be used to display PFS time graphically. Cox proportional hazards model will be used to estimate hazard ratio and the corresponding 80% confidence interval. Median PFS event times and 80% confidence interval will be computed as well.

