### 10.5. Efficacy Analysis

### 10.5.1. Primary Efficacy Analysis

PFS is defined as the time from randomization to the first documented radiographical progression of disease using RECIST v1.1 or death from any cause, whichever comes first. Details of censorship will be thoroughly explained in the SAP. PFS will be analyzed based on investigator assessed. The primary endpoint will be based on the investigator assessment of disease progression.

The Kaplan-Meier estimates will be used to determine median PFS and 80% CI for each treatment group. A stratified log-rank will be used to test for PFS distribution differences. A stratified Cox proportional hazards model will be used to estimate the hazard ratio and corresponding 80% confidence intervals. Stratification factors include: Geographic region (US, non-US) and bone-only disease (yes, no).

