#### Table 3.1 Documented Disease Progression and Censoring

Situation	Date of	Outcome
Inadequate baseline tumor assessment No on-treatment assessment and no death prior to first scheduled assessment	Randomization	Censored
Death or documented disease progression after ≥ 2 consecutively missed and/or not evaluable scheduled tumor assessments	Last tumor assessment documenting no disease progression	Censored
Alive, on-treatment, and no documented disease progression	Last tumor assessment documenting no disease progression	
Documented disease progression (on, prior to, or $\leq 30$ days after treatment discontinuation)	First tumor assessment documenting disease progression	Progression (Event)
New anticancer treatment $\leq$ 30 days after treatment discontinuation without disease progression	Last tumor assessment documenting no disease progression prior to starting the new anticancer treatment	Censored
Treatment discontinuation due to toxicity, undocumented disease progression, or any other reason	Last tumor assessment documenting no disease progression prior to discontinuation	Censored
Death prior to first scheduled assessment	Death	Death (Event)
Death without documented disease progression and $\leq 30$ days after treatment discontinuation	Death	Death (Event)

Note: Follow-up scans can be performed up to 4 weeks from last treatment dose date via protocol

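### The SAP censors at randomisation an unscanned patient who dies between the first and second planned scans, where the protocol counts that death as a PFS event

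*SAP*

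**What the plan says.** **Protocol.** Section 10.5.1 defines a PFS event as "first documented radiographical progression of disease using RECIST v1.1 or death from any cause". The synopsis (statistical considerations) limits this for missed scans: "Patients with documented PD or death after an unacceptable long interval (i.e., 2 or more missed or indeterminate scheduled assessments) will be censored". It censors on the randomisation date only when there is no valid tumour evaluation at randomisation, which is a baseline condition. It has no separate rule for a patient whose first post-baseline scan is missing.

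**SAP text, section 3.1.** "Patients with no tumor assessment after dosing will be censored at the date of randomization unless death occurred prior to the first planned assessment". A separate bullet reads "Patients with at least one on-study disease assessment who discontinue treatment without documented disease progression or death are censored". Its two exceptions follow; one keeps a death or progression within 30 days of stopping treatment as an event.

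**SAP Table 3.1.** The first row covers "No on-treatment assessment and no death prior to first scheduled assessment" and gives censoring at randomisation. The long-gap row covers "Death or documented disease progression after ≥ 2 consecutively missed and/or not evaluable scheduled tumor assessments" and gives censoring at the last scan. The last row begins "Death without documented disease progression and", applies up to 30 days after treatment discontinuation, and gives an event on the date of death. It does not require an earlier scan.

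**The concern.** For one type of patient the plan gives two outcomes: adequate baseline, no post-baseline scan, and death after the first planned scan date but before two scans have been missed. The protocol says event. The SAP no-scan rule says censored on day 1. If the death falls on treatment or within 30 days of stopping, two rows of the same SAP table disagree and no order of precedence is stated.

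The SAP's result also departs from its own tolerance of a single missed scan. A patient scanned at week 8 who misses week 16 and dies on treatment in week 18 is an event. A patient who misses week 8 and dies on treatment in week 10 contributes nothing.

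These are early deaths. If the missed scan is linked to worsening disease, the censoring depends on prognosis. If the unscanned deaths are unevenly split between arms, the hazard ratio shifts. A choice between table rows made after unblinding would be open to criticism.

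**Working it through.** **1. One patient under each rule.** Scans are every 8 weeks (Protocol 7.7), so the first two are planned for days 56 and 112. Suppose an adequate baseline, no later scan, no new therapy, and death on treatment 70 days after randomisation. SAP 3.1 derives PFS as (date − randomisation + 1)/30.4375.

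| Rule | Outcome | PFS (months) |
|---|---|---|
| Protocol synopsis and 10.5.1 (one scan missed) | Event | (70+1)/30.4375 = 2.33 |
| SAP 3.1 text; Table 3.1 first row | Censored | (0+1)/30.4375 = 0.03 |
| SAP Table 3.1 long-gap row | Not triggered (one scan missed) | – |
| SAP Table 3.1 last row | Event | 2.33 |

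For deaths from day 57 to day 111, the event time would be 1.91 to 3.68 months in place of censoring at 0.03.

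**2. Does another analysis restore the death?** PFS by independent review uses the same censoring rules (SAP 3.3). The SAP's censors-as-events analysis covers only the seribantumab arm and uses the censoring date (5.5.2), so the death would be placed on day 1. TTP uses the date of death for a patient who dies before a first scan (Protocol 10.5.2, SAP 3.4). She therefore has 2.33 months of TTP follow-up and 0.03 months of PFS.

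**3. Scale: the plan's own event count.** Inputs from Protocol 10.2: HR 0.57, one-sided 0.10, 80% power, 1:1. Schoenfeld: 4(1.2816 + 0.8416)²/(ln 0.57)² = 18.03/0.316 = 57.1, so 58, as stated. Power at 58 events is 0.805.

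**4. How many patients (illustration).** Protocol 1.1 cites median survival of 18 to 36 months. Assuming exponential survival, the chance of death from day 56 to day 112 is exp(−1.84 ln2/m) − exp(−3.68 ln2/m), with 1.84 and 3.68 months the two scan dates.

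| Median m (months) | Probability | Of 80 |
|---|---|---|
| 18 | 6.4% | 5.1 |
| 24 | 4.9% | 3.9 |
| 36 | 3.4% | 2.7 |

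The documents do not say how many such patients would be unscanned. Assuming 10% to 50% gives 0.3 (10% of 2.7) to 2.5 (50% of 5.1), so about 0 to 3 patients.

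**5. Effect on power.** With a fixed data cut-off, losing 1, 2 or 3 of 58 events gives power 0.800, 0.794 or 0.789. The analysis is event-driven, so the more likely result is a later cut-off.

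**6. Effect on the hazard ratio.** Simulated trials had 40 patients per arm, exponential PFS with medians 4 and 7 months, uniform accrual over 16 months and cut-off at 58 events. Two events in the week 8 to 16 window of one arm were recensored at day 1.

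| Arm losing two events | Events in arm | Change in HR |
|---|---|---|
| Control | about 32 | up about 3.5% |
| Seribantumab | about 26 | down about 6.5% |

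The standard error of log HR is about 2/√58 = 0.26. The shifts (about 0.035 and 0.066 on the log scale) are therefore about 0.13 and 0.25 of a standard error. The significance boundary lies near exp(−1.2816 × 2/√58) = 0.71, so they would matter only for a result close to it.

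**The case against.** **The protocol leaves censoring to the SAP.** Section 10.5.1 refers the details there, and section 10 lets the SAP modify the plan. This softens the difference between the documents. But section 10 also requires major changes to the primary endpoint or its analysis to appear in an amendment, and delegation does not settle a disagreement inside the SAP's own table.

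**The SAP text can be read consistently.** The 30-day death exception sits under a bullet for patients with at least one scan, and never-scanned patients have their own bullet. On that reading the last table row only summarises the exception. This stands for the text: a reader might infer that the whole SAP contradicts itself, but the clear conflict is between table rows. The row carries no such limit, and reading one in leaves the conflict with the protocol.

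**The scope is narrow.** A reader might infer that every unscanned death after week 8 is mishandled against the protocol. It is not: after two missed scans the protocol also censors, and with no post-baseline scan the date falls back to about baseline. Nor does the last table row cover deaths more than 30 days after stopping.

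**Few patients will qualify.** Protocol 4.4 asks for a scan at treatment discontinuation, and 7.7 asks for an unscheduled scan when progression is suspected. Both reduce the group. That these patients miss the scan because they are deteriorating is plausible, but the documents do not say so.

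**The SAP describes another design.** It names a different protocol number and a phase 3, 2:1 trial of exemestane or fulvestrant with 195 events. This makes the edit part of a larger alignment. It does not make the rule right.

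**Conclusion.** The point holds for unscanned deaths between the first planned scan and the second missed one, about weeks 8 to 16. There the SAP no-scan rule turns a protocol-defined event into zero follow-up. For deaths on treatment or within 30 days of stopping, the last row of Table 3.1 contradicts it as well.

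The likely size is small: about 0 to 3 of 80 patients, resting on exponential survival and an assumed 10% to 50% unscanned. The loss of power is negligible; the issue is possible bias. Two such deaths in one arm, an unfavourable split, move the hazard ratio by about 3.5% or 6.5%. A reader might infer about 7% for the control arm from the ratio 32/30, but that overstates it, because censoring on day 1 removes follow-up time as well as events. The textual conflict is certain; the numerical effect is an illustration. The rule should be corrected before unblinding.

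**What to change.** Replace the no-scan bullet in SAP 3.1 and the matching entry in the first row of Table 3.1 with a rule such as:

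> No post-baseline assessment and no new anti-cancer therapy: death before two consecutive scheduled assessments have been missed is an event on the date of death. Otherwise, or if new anti-cancer therapy was started first, censored at randomisation.

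Make the last row of Table 3.1 subject to the same two-missed-assessments and new-therapy rules. Otherwise an unscanned on-treatment death after two missed scans would still receive two outcomes.

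State how missed assessments are counted in the analysis: from randomisation with the ±5-day window of Protocol 7.7. SAP 3.1 counts from first dose with ±7 days, and the schedule table in Protocol 6.1 also uses first dose with ±1 week, so these passages must be reconciled.

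The cost is one rule, two table rows and one definition, within the wider alignment of the SAP to this protocol. It needs no extra patients or data.
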